#### **6.2.2.2 Rules for Withholding or Restarting**

- AMG 994, and AMG 404 if the subject is on combination therapy, should be withheld for any DLT or any adverse event that meets the criteria of a DLT but occurs outside of the DLT windows
- AMG 994, and AMG 404 if the subject is on combination therapy, should be withheld for potential hepatotoxicity as detailed in [Table 11-2](#)
- AMG 404 alone should be withheld for immune-mediated adverse reactions as detailed in [Table 11-3](#)
- AMG 994 and/or AMG 404 should be withheld for infusion-related reactions as specified in [Table 11-4](#)

For adverse events not addressed by [Table 11-2](#), [Table 11-3](#) and [Table 11-4](#), AMG 994 and AMG 404 dosing can be resumed if the applicable event resolves to grade  $\leq 1$  or otherwise resolves to subject's baseline grade within 2 weeks. The restarting of therapy should be deemed appropriately safe by the investigator and Medical Monitor. For restart criteria following hepatotoxicity, immune-mediated reactions, and infusion-related reactions, refer to [Table 11-2](#), [Table 11-3](#) and [Table 11-4](#), respectively. For immune-mediated hepatitis, if [Table 11-2](#) and [Table 11-3](#) are both applicable, [Table 11-2](#) is to take precedence.

Subjects should not be restarted with AMG 994 and/or AMG 404 if the following treatment-related adverse events occur:

- Any grade 4 adverse events except those not considered DLT, OR
- Adverse event criteria are met for permanent withholding of AMG 994 and/or AMG 404 due to potential hepatotoxicity, immune-mediated reaction or infusion related reaction ([Table 11-2](#), [Table 11-3](#), or [Table 11-4](#), respectively). For immune-mediated hepatitis, if [Table 11-2](#) and [Table 11-3](#) are both applicable, [Table 11-2](#) is to take precedence.

If a subject experiences an adverse event meeting withholding or discontinuation criteria above from AMG 404, and if the subject is experiencing clinical benefit with AMG 994 monotherapy, a decision to have the subject continue with AMG 994 monotherapy alone, may be considered by the Amgen medical monitor in consultation with the investigator.

The reason for dose change of AMG 994 and/or AMG 404 is to be recorded on each subject's CRF.

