	Grade 3 (increase of 7 or more stools per day over baseline, incontinence; hospitalization indicated, severe increase in ostomy output compared with baseline, limiting self-care ADL)			
	Grade 4 (life-threatening consequences; urgent intervention indicated)	Permanently discontinue		

Page 2 of 8

Footnotes defined on last page of this table

**Table11-3. Dose Modification and Toxicity Management Guidelines for Immune-related Adverse Reactions Associated With AMG 404\***

Immune-related Adverse Reactions	Severity (CTCAE Grade Version 5.0 or Specific Conditions)	AMG 404 Dose Modification	Management with Corticosteroids and/or Other Therapies	Monitor & Follow-up
Hepatitis	Grade 2 (asymptomatic, AST or ALT > 3.0 to $\leq$ 5 x ULN and/or total bilirubin > 1.5 to $\leq$ 3 x ULN [for patients with values < ULN at baseline])	Withhold	Administer corticosteroids at an initial dose of 0.5 to 1 mg/kg/d prednisone (or equivalent) followed by taper.	Monitor with liver function tests more frequently until returned to baseline or stable.
	Grade 3 (symptomatic liver dysfunction, fibrosis by biopsy, compensated cirrhosis, reactivation of chronic hepatitis [AST or ALT 5-20 x ULN and/or total bilirubin 3-10 x ULN])	Permanently discontinue	Administer corticosteroids at an initial dose of 1 to 2 mg/kg/d prednisone (or equivalent) followed by taper. Consider mycophenolate mofetil if refractory to corticosteroids or no improvement after 3 days.	
	Grade 4 (decompensated liver function eg, ascites, coagulopathy, encephalopathy, coma [AST or ALT > 20 x ULN and/or total bilirubin > 10 x ULN])		Administer corticosteroids at an initial dose of 2 mg/kg/d prednisone (or equivalent) followed by taper. Consider mycophenolate mofetil if refractory to corticosteroids or no improvement after 3 days.	

Page 3 of 8

Footnotes defined on last page of this table

**Table 11-3. Dose Modification and Toxicity Management Guidelines for Immune-related Adverse Reactions Associated With AMG 404\***

Immune-related Adverse Reactions	Severity (CTCAE Grade Version 5.0 or Specific Conditions)	AMG 404 Dose Modification	Management with Corticosteroids and/or Other Therapies	Monitor & Follow-up

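### Precedence of Table 11-2 turns a permanent AMG 404 stop into a listed hold at isolated AST/ALT above 8 to 20 × ULN, and a Hy's Law DLT with raised baseline AST/ALT misses the permanent rule

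*Protocol*

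**What the plan says.** Two tables govern liver events.

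- **Table 11-3** (Section 11.10) covers immune-related reactions and acts on AMG 404 only: "AMG 404 alone should be withheld for immune-mediated adverse reactions as detailed in" that table. Grade 3 hepatitis, bracketed as "AST or ALT 5-20 x ULN and/or total bilirubin 3-10 x ULN", means permanent discontinuation. Grade 2 means a hold, and its bracket is limited to subjects "for patients with values < ULN at baseline".
- **Table 11-2** (Section 11.7) covers potential hepatotoxicity and acts on both drugs. AST/ALT leads to a temporary hold above 8 × ULN; between 5 and 8 × ULN if it lasts at least 2 weeks or cannot be monitored; and above 3 × ULN with hepatitis symptoms. Bilirubin above 3 × ULN is also a hold. The permanent column needs bilirubin above 2 × ULN or INR above 1.5, together with AST/ALT above 3 × ULN and a baseline below ULN.

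Section 6.2.2.2 links them: "For immune-mediated hepatitis, if [Table 11-2](#) and [Table 11-3](#) are both applicable, [Table 11-2](#) is to take precedence". The sentence appears once with the restart criteria and once inside the no-restart list. That list also bars restart after treatment-related events described as "Any grade 4 adverse events except those not considered DLT, OR" a permanent criterion being met in one of the tables.

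For events that the tables do not address, "AMG 994 and AMG 404 dosing can be resumed if the applicable event resolves to grade" 1 or lower "or otherwise resolves to subject's baseline grade within 2 weeks". The condition is: "The restarting of therapy should be deemed appropriately safe by the investigator and Medical Monitor".

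Section 6.2.1 makes any Hy's Law case a DLT (AST/ALT at least 3 × ULN, bilirubin above 2 × ULN, no cholestasis, no clear alternative explanation), with no baseline condition. Criterion 112 admits AST/ALT up to 3 × ULN, or 5 × ULN with liver metastasis.

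**The concern.** (a) Where both tables apply to an isolated transaminase rise, precedence selects the weaker listed action on AMG 404. It can also invert the order of severity, so that a larger rise is listed as a hold while a smaller, brief one is a permanent stop.

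(b) The permanent column of Table 11-2, and the never-rechallenge rule in Section 11.7 that refers to it, both depend on a normal baseline. A subject enrolled with raised AST/ALT who then has a Hy's Law DLT falls outside both.

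This is a first-in-human combination. Two sites following the text in good faith could handle the same serious liver event differently, according to how they read one entry in a list of causes (a) or according to baseline AST/ALT alone (b).

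**Working it through.** The plan states no figure to reproduce. The check applies the thresholds of both tables to the same event.

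**(a) Immune-mediated hepatitis.** Inputs: normal baseline, bilirubin 1 × ULN, INR 1.0. The bracketed range is taken as defining grade.

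| AST/ALT (× ULN) and course | Table 11-2 | Table 11-3 (AMG 404) | Listed AMG 404 action under precedence |
|---|---|---|---|
| 6; brief, asymptomatic, monitored | no row | permanent | permanent |
| 6; at least 2 weeks, or symptomatic, or cannot be monitored | hold | permanent | hold |
| 8.1, 12 or 20; any course | hold | permanent | hold |
| 21; any course | hold | permanent (grade 4) | hold, but the separate grade 4 bar on restart applies if it is treatment-related |

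The downgrade thus covers values above 8 and up to 20 × ULN, and 5-8 × ULN in the longer, symptomatic or unmonitored courses. Its limits are:

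- Normal baseline with bilirubin 2.5 × ULN or INR 1.6: at AST/ALT 6, 10 and 18 × ULN both tables are permanent, so nothing is lost.
- AST/ALT 4 × ULN, normal baseline, bilirubin 2.5 × ULN or INR 1.6: Table 11-2 is permanent and Table 11-3 a hold. Here precedence is the stricter choice.

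Over AST/ALT 6, 10 and 18 × ULN and four courses (brief; at least 2 weeks; symptomatic; unmonitored), the listed action changes from permanent to hold in 3 + 4 + 4 = 11 of 12 scenarios. If grade 3 instead requires symptomatic liver dysfunction, only the symptomatic course has a Table 11-3 stop to displace: 3 × 1 = 3 of 12. The inversion also disappears on that reading.

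**(b) Hy's Law DLT.** Actions under Table 11-2:

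| AST/ALT, bilirubin (× ULN) | Baseline AST/ALT < ULN | Baseline ≥ ULN, brief and asymptomatic | Baseline ≥ ULN, symptomatic |
|---|---|---|---|
| 4, 2.5 | permanent | no row | hold |
| 4, 3.5 | permanent | hold | hold |
| 6, 2.5 | permanent | no row (Table 11-3 stops AMG 404 if immune-mediated) | hold |
| 9, 2.5 | permanent | hold | hold |

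No Hy's Law combination with raised baseline reaches the permanent column. For AST/ALT 3.5 and 4.5 × ULN with bilirubin 2.5 × ULN, over four courses (2 × 4 = 8 scenarios), normal baseline gives 8 of 8 permanent. Raised baseline gives 0 of 8 permanent, 6 of 8 with no row and 2 of 8 (symptomatic) on hold. At exactly 3 × ULN the permanent column is missed at any baseline, because it requires a value above 3.

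Example: AST rises from 1.5 to 4.5 × ULN (4.5 / 1.5 = 3.0 times baseline) with bilirubin 2.5 × ULN and no symptoms. Section 6.2.2.2 holds both drugs because it is a DLT, but Table 11-2 has no row for it. DLT status alone does not exclude further dosing: Section 6.2.2.1 allows a reduced dose after a DLT when there is clinical benefit. If the event is called immune-mediated and the Table 11-3 grade 2 bracket is read analyte by analyte, a normal-baseline bilirubin adds an AMG 404 hold, still not a permanent stop.

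All counts are scenarios on a chosen grid, not subjects.

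**The case against.** The strongest reply is that neither gap leads easily to restart.

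On (a), Section 11.7 applies Table 11-2 only where no other cause has been found. It ties rechallenge to discovering such a cause, recovery of the laboratory values and unanimous agreement of subject, investigator and sponsor. If AMG 404 hepatitis does not count as an alternative cause, the rechallenge condition is unmet and AMG 994 is held as well. If it does count, Table 11-2 drops out, the tables are no longer both applicable, and the Table 11-3 permanent stop governs. Either reading largely blocks AMG 404 restart. This stands, so a reader should not infer from 11 of 12 that AMG 404 would be restarted in those scenarios; the count concerns table entries and depends on the bracket reading. What remains is conflicting instruction: Section 11.7 lists autoimmune hepatitis among alternative causes without saying whether AMG 404 hepatitis belongs there, and precedence is written for that very event.

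On (b), a reader might infer that a Hy's Law case with raised baseline can simply restart both drugs under the 2-week fallback. The documents do not support that. The paragraph containing the fallback sends hepatotoxicity restarts to Table 11-2. Section 6.2.1 sends Hy's Law cases to Sections 6.2.3 and 11.7, where rechallenge needs the alternative cause that a Hy's Law case by definition lacks. With bilirubin above 3 × ULN, AST/ALT above 8 × ULN, or symptoms with AST/ALT above 3 × ULN, a Table 11-2 hold applies and the fallback is closed. Against this, Table 11-2 has no restart column and no raised-baseline row, so in the narrow band the event is literally not addressed by it. Even then, the investigator and Medical Monitor must judge restart safe.

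**Conclusion.** The concern holds as a defect of the text, in two parts.

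(a) For immune-mediated hepatitis with AST/ALT above 8 to 20 × ULN, bilirubin ≤2 × ULN and INR ≤1.5, precedence replaces a permanent AMG 404 stop with a hold. If the bracket defines grade 3, the worse injury gets the lighter listed action. Appendix 7 constrains actual restart, so the consequence is contradictory instruction rather than free rechallenge.

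(b) A Hy's Law DLT with baseline AST/ALT at or above ULN loses both the explicit permanent stop and the explicit never-rechallenge bar. At AST/ALT 3-5 × ULN with bilirubin above 2 to 3 × ULN and no symptoms, no Table 11-2 row applies and restart is not expressly barred. The fallback is available only on a literal reading that the routing sentences contradict. Close observation under Section 11.7 still applies but does not bar restart.

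The documents do not show how many subjects either part would affect.

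**What to change.** 1. Replace both precedence sentences in Section 6.2.2.2 so that, when both tables apply to immune-mediated hepatitis, the more restrictive action and restart condition govern each drug. Raised baselines need a guard: a rise from 4.8 to 5.2 × ULN in a subject with liver metastasis (5.2 / 4.8 = 1.08 times baseline) would otherwise end AMG 404, as the current text already does when the rise is brief. Setting the Table 11-3 grade 3 floor for such subjects at the higher of 5 × ULN and a sponsor-chosen multiple of baseline would avoid this.
2. State in Section 11.7 that hepatitis attributed to study drug is not an alternative cause, either for leaving Table 11-2 or for permitting rechallenge.
3. Add a raised-baseline permanent row to Table 11-2 for cases meeting the Section 6.2.1 Hy's Law definition, with a baseline multiple. Section 11.7 already uses 2-fold for close observation, and the 3.0-fold example above would be caught. State that Hy's Law cases are never rechallenged and are outside the 2-week fallback. As worded, that bar would also cover a Hy's Law case below the multiple, and the sponsor should confirm that this is intended.

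The cost is a text amendment with no new tests, plus a sponsor decision on the multiple. Some subjects would lose the option of rechallenge with AMG 404 or AMG 994.

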#### **6.2.3 Hepatotoxicity Stopping and Rechallenge Rules**

Refer to Section [11.7](#) for details regarding drug-induced liver injury guidelines, as specified in the *Guidance for Industry Drug-Induced Liver Injury: Premarketing Clinical Evaluation, July 2009*.

#### **6.3 Preparation/Handling/Storage/Accountability**

Guidance and information on preparation, handling, storage, accountability, destruction, or return of the investigational product during the study are provided in the Modular IPIM.

#### **6.4 Treatment Compliance**

Compliance to treatment and the corresponding assessments should be followed according to the Schedule of Activities (Section [1.3](#)) and the Study Assessments and Procedures (Section [8](#)).

#### **6.5 Treatment of Overdose**

The effects of overdose of AMG 994 and AMG 404 are not known.

#### **6.6 Prior and Concomitant Treatment**

##### **6.6.1 Prior Treatment**

Prior therapies that were being taken/used from initial diagnosis through the time of consent will be collected.

##### **6.6.2 Concomitant Treatment**

Throughout the study, investigators may prescribe any concomitant medications or treatments deemed necessary to provide adequate supportive care except for those listed in Section [6.1.7](#).

Concomitant therapies are to be collected from informed consent through the end of study.

### **7. Discontinuation Criteria**

Subjects have the right to withdraw from investigational product and/or other protocol-required therapies, protocol procedures, or the study as a whole at any time and for any reason without prejudice to their future medical care by the physician or at the institution.

The investigator and/or sponsor can decide to withdraw a subject(s) from investigational product, device, and/or other protocol-required therapies, protocol procedures, or the

study as a whole at any time prior to study completion for the reasons listed in Section 7.1, Section 7.2.1, and Section 7.2.2.

### **7.1 Discontinuation of Study Treatment**

Subjects (or a legally acceptable representative) can decline to continue receiving investigational product and/or other protocol-required therapies or procedures at any time during the study but continue participation in the study. If this occurs, the investigator is to discuss with the subject the appropriate processes for discontinuation from investigational product or other protocol-required therapies and must discuss with the subject the possibilities for continuation of the Schedule of Activities (see Section 1.3) including different options of follow-up (eg, in person, by phone/mail, through family/friends, in correspondence/communication with other treating physicians, from the review of medical records) and collection of data, including endpoints and adverse events, and must document this decision in the subject's medical records. Subjects who have discontinued investigational product and/or other protocol-required therapies or procedures should not be automatically removed from the study. Whenever safe and feasible, it is imperative that subjects remain on-study to ensure safety surveillance and/or collection of outcome data.

Subjects may be eligible for continued treatment with Amgen investigational product(s) and/or other protocol-required therapies by a separate protocol or as provided for by the local country's regulatory mechanism, based on parameters consistent with Section 11.3.

Reasons for early removal from protocol-required investigational product(s) or procedural assessments may include any of the following:

- Decision by Sponsor
- Lost to follow-up
- Death
- Adverse event
- Subject request
- Ineligibility determined
- Protocol deviation
- Non-compliance
- Disease progression
- Pregnancy

## **7.2 Discontinuation From the Study**

Withdrawal of consent for a study means that the subject does not wish to receive further protocol-required therapies or procedures, and the subject does not wish to or is unable to continue further study participation. Subject data up to withdrawal of consent will be included in the analysis of the study, and where permitted, publicly available data can be included after withdrawal of consent. The investigator is to discuss with the subject appropriate procedures for withdrawal from the study, and must document the subject's decision to withdraw in the subject's medical records.

If a subject withdraws from the study, he/she may request destruction of any samples taken and not tested, and the investigator must notify Amgen accordingly (see Section 11.6 for further details). Refer to the Schedule of Activities (Section 1.3) for data to be collected at the time of study discontinuation and follow-up and for any further evaluations that need to be completed.

### **7.2.1 Reasons for Removal From Washout Period, Run-in Period, or Invasive Procedures**

This section is not applicable.

### **7.2.2 Reasons for Removal From Study**

Reasons for removal of a subject from the study are:

- Decision by sponsor
- Withdrawal of consent from study
- Death
- Lost to follow-up

### **7.3 Lost to Follow-up**

A subject will be considered lost to follow-up if he or she repeatedly fails to return for scheduled visits and is unable to be contacted by the study site.

The following actions must be taken if a subject fails to return to the clinic for a required study visit:

- The site must attempt to contact the subject and reschedule the missed visit as soon as possible and counsel the subject on the importance of maintaining the assigned visit schedule and ascertain whether or not the subject wishes to and/or is able to continue in the study.
- In cases in which the subject is deemed lost to follow-up, the investigator or designee must make every effort to regain contact with the subject (where possible, 3 telephone calls and, if necessary, a certified letter to the subject's last known

mailing address or local equivalent methods). These contact attempts are to be documented in the subject's medical record.

- If the subject continues to be unreachable, he/she will be considered to have withdrawn from the study with a primary reason of lost to follow-up.
- For subjects who are lost to follow-up, the investigator can search publicly available records where permitted to ascertain survival status. This ensures that the data set(s) produced as an outcome of the study is/are as comprehensive as possible.

## **8. Study Assessments and Procedures**

Study procedures and their time points are summarized in the Schedule of Activities (see Section 1.3).

As protocol waivers or exemptions are not allowed if an enrolled subject is subsequently determined to be ineligible for the study, this must be discussed with the sponsor immediately upon occurrence or awareness to determine if the subject is to continue or discontinue study treatment.

Adherence to the study design requirements, including those specified in the Schedule of Activities, is essential and required for study conduct.

### **8.1 General Study Periods**

#### **8.1.1 Screening, Enrollment and/or Randomization**

Informed consent must be obtained before completing any screening procedure or discontinuation of standard therapy for any disallowed therapy. After the subject has signed the informed consent form, the site will screen the subject in order to assess eligibility for participation. The screening window is up to 28 days prior to day 1.

All screening evaluations must be completed and reviewed to confirm that potential subjects meet all eligibility criteria. The investigator will maintain a screening log to record details of all subjects screened and to confirm eligibility or record reasons for screening failure, (see Section 5.4) as applicable.

If a subject has not met all eligibility criteria at the end of the screening period, the subject will be registered as a screen fail. Screen fail subjects may be eligible for re-screening up to 3 additional times.

Rescreen subjects must first be registered as screen failures and subsequently registered as rescreens. Once the subject is registered as rescreened, a new 28 day screening window will begin. Subjects will retain the same subject identification number assigned at the original screening. If the rescreening period begins more than 30 days

after the original signing of the informed consent form, all screening procedures, including informed consent, must be repeated.

#### **8.1.2 Treatment Period**

Visits will occur per the Schedule of Activities (see Section 1.3). On-study visits may be completed within 1 day/week. The date of the first dose of AMG 994 or AMG 404 is defined as day 1. All subsequent doses and study visits will be scheduled based on the day 1 date. Administration of AMG 994 and/or AMG 404 is to be administered after all safety assessments have been completed and reviewed during each visit that it is required.

#### **8.1.3 Safety Follow-up**

Upon permanent discontinuation from the study treatment for any reason, a safety follow-up visit will be performed at 30 (+7) days and 140 days ( $\pm 1$  week) after the last dose of protocol required therapies. These visits include adverse event/serious adverse event assessment, a physical exam, blood work (chemistry; coagulation; complete blood count [CBC]; adrenocortiopic hormone [ACTH]; anti-neutrophil cytoplasmic antibodies [ANCA], anti-nuclear antibodies [ANA], pregnancy test), and urinalysis.

The chemistry includes albumin, alkaline phosphatase, ALT, AST, blood urea nitrogen (BUN)/total urea, calcium, chloride, creatinine, glucose, potassium, sodium, total bilirubin, total protein, thyroid stimulating hormone (TSH), and free T4.

